### **6.1.5. Sparsentan + SGLT2 Inhibitor Sub-study Endpoints**

For the Sub-study, the baseline visit (Day 1) is defined as the visit upon which eligibility is assessed.

#### **6.1.5.1. Safety Endpoints**

Safety evaluations include the following:

- Changes from Sub-study baseline in body weight, vital signs, physical examinations, peripheral edema, and clinical laboratory parameters at each visit.
- The incidence of TEAEs during the Sub-study period.

#### **6.1.5.2. Efficacy Endpoints**

Endpoints include, but are not limited to:

- The mean percent change from Sub-study baseline in UP/C and UA/C based on a 24-hour urine sample at the next scheduled visit.
- Achievement of urinary protein excretion  $<0.3$  g/day at the next scheduled visit.
- Change in absolute and percent change from Sub-study baseline in eGFR at the next scheduled visit.

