**Open-label Extension Period Endpoints:**

Endpoints for the open-label extension period include, but are not necessarily limited to the following:

- The absolute and percent change from Week 114 in eGFR at each visit.
- The percent change from Week 114 in UP/C at each visit.
- Changes from Week 114 in QoL at each visit.
- Changes from Week 114 in body weight, vital signs, physical examinations, peripheral edema, and clinical laboratory parameters.
- Changes from Week 114 in lipid profile (total cholesterol and triglycerides, low-density lipoprotein, and high-density lipoprotein).
- The incidence of TEAEs during the open-label extension period.

NAME OF COMPANY: Traverse Therapeutics, Inc.
	
NAME OF FINISHED PRODUCT: sparsentan tablets

Sparsentan + SGLT2 Inhibitor Sub-study:
 
For the Sub-study, the baseline visit (Day 1) is defined as the visit upon which eligibility is assessed.
 
Safety Endpoints:
 
Safety evaluations include the following:
 
 
• Changes from Sub-study baseline in body weight, vital signs, physical examinations, peripheral edema, and clinical laboratory parameters at each visit.
 
• The incidence of TEAEs during the Sub-study period.
 
 
Efficacy Endpoints:
 
Endpoints include, but are not limited to:
 
 
• The mean change from Sub-study baseline in UP/C and UA/C based on a 24-hour urine sample at the next scheduled visit.
 
• Achievement of urinary protein excretion <0.3 g/day at the next scheduled visit.
 
• Change in absolute and percent change from Sub-study baseline in eGFR at the next scheduled visit.
 
	

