P-gp	P-glycoprotein
PK	Pharmacokinetic(s)
PP	Per Protocol (analysis set)
PRO	Patient-reported outcome
QoL	Quality of life
RAAS	Renin-angiotensin-aldosterone system
RRT	Renal replacement therapy
SAE	Serious adverse event
SAP	Statistical analysis plan
SAS®	Statistical Analysis System
SGLT2	Sodium-glucose cotransporter-2
SmPC	Summary of Product Characteristics
SOP	Standard operating procedure
SUSAR	Suspected, unexpected serious adverse reaction
TEAE	Treatment-emergent adverse event
ULN	Upper limit of normal
UA/C	Urine albumin/creatinine ratio
UP/C	Urine protein/creatinine ratio
US	United States
USPI	US Prescribing Information
WOCBP	Women of childbearing potential

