- f Sample will be collected 24 hours immediately prior to the visit. Patients who forget to collect this sample the 24 hours immediately prior to the visit may collect and return it within the visit window. Protein and albumin excretion, creatinine, sodium, and urea will be measured from this sample.
- g Calculated using the CKD-EPI formula based on age, sex, race, and serum creatinine values from the visit.
- h A blood sample for plasma PK will be drawn prior to study medication administration. Once EOT is completed for a patient, PK samples will not be collected.
- i WOCBP only. Urine pregnancy tests will be performed at all visits and monthly between visits. A positive urine pregnancy test will be confirmed by a serum test.
- j QoL questionnaires should be completed prior to any other assessment. The questionnaires will be the KDQoL-36 (which consists of the first 12 questions of the SF-12 and 24 questions [questions 13-36] from the KDQoL-36) and the EQ-5D-5L. If the questionnaires were NOT completed at baseline for the double-blind period (Day 1), the patient should not complete them for the rest of the double-blind period. Patients participating in the open-label extension period who did not complete the questionnaires at Day 1 of the double-blind period should complete them at Week 114 (as baseline assessments for the open-label extension) and throughout the open-label extension.
- k Sites will provide WOCBP with enough tests to conduct pregnancy testing once per month until the next scheduled study visit and will contact these patients monthly to confirm that the pregnancy test has been performed and the results are negative.
- l Patients who may be eligible for the open-label extension period should sign the open-label extension period informed consent form at Week 110. Patients may also sign the OLE period informed consent form at Week 114, if not completed previously at Week 110.

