- m Dispense study medication. Patients will be instructed to take their study medication in the clinic on the day of office visits. All other days, study medication should be taken prior to the morning meal. Patients will be instructed to swallow the capsules whole. Patients will also be instructed to avoid drinking or eating anything that contains grapefruit, Seville oranges (bitter oranges often used as marmalade), starfruit (carambola), or pomelo/shaddock throughout the study. The patient will be instructed to bring all sparsentan tablets and their original containers to the next clinic visit.

**Table 15.1-3. Open-label Extension Period and Sparsentan + SGLT2 Inhibitor Sub-study: Schedules of Study Events from Week 110 Through Week 186**

Week	Open-label Treatment								
	Week 110 Screening	Week 114 Baseline/ Day 1	Week 116	Week 126	Week 138	Week 150	Week 162	Week 174	Week 186
Visit	15	16	17	18	19	20	21	22	23
Visit Window	± 14 days	- 7/ + 14 days	- 7/ + 14 days	± 28 days	± 28 days	± 28 days	± 28 days	± 28 days	± 28 days
Informed Consent for OLE a	X	X							
Informed Consent for Sub-Study (Baseline Sub-study Visit) and Randomization m				As early as Week 126 (Visit 18) but no later than Week 258 (Visit 29)					
Full Physical Examination	X								
Targeted Physical Examination		X	X	X	X	X	X	X	X
Peripheral Edema Assessment b	X	X	X	X	X	X	X	X	X
Vital Signs c	X	X	X	X	X	X	X	X	X
Clinical Laboratory Assessments Panel A d	X	X		X	X	X	X	X	X
Clinical Laboratory Assessments Panel B e	X	X	X						
Lipid Panel f	X	X				X	X	X	X
NT-proBNP	X	X	X	X	X	X	X	X	X
Quantitative Urinalysis (24-hour collection) g	X	X		X	X	X	X	X	X
QoL Questionnaire h	X	X		X	X	X	X	X	X
Pregnancy Test i	X	X		X	X	X	X	X	X
Dispense Urine Pregnancy Tests i			X	X	X	X	X	X	X
Biorepository Samples (blood and urine, if consented)	X	X		X	X	X	X	X	X
Study Medication Dispensing j,1		X	X	X	X	X	X	X	X
Study Medication Accountability a		X	X	X	X	X	X	X	X
12-lead Electrocardiogram k,o	X	X							
Adverse Event Assessment	-----Continuous Monitoring-----								
Concomitant Medications/Therapies	-----Continuous Monitoring-----								

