- d Includes clinical chemistry (serum sodium, potassium, chloride, bicarbonate, total protein, albumin, calcium, phosphate, glucose, cystatin, uric acid, BUN, creatinine [including calculation of eGFR], bilirubin [total, direct, and indirect], ALT, AST, ALP, gamma glutamyltransferase, creatine kinase, and amylase); hematology (red blood cells, hemoglobin, hematocrit, MCV, MCH, MCHC, platelets, WBC, and WBC differential [percentage and absolute: neutrophils, eosinophils, basophils, lymphocytes, and monocytes]); and routine urinalysis (color, appearance, and dipstick [pH, specific gravity, protein, glucose, ketones, bilirubin, blood, urobilinogen, and leukocyte esterase]). All chemistry and hematology analytes are shown in [Section 15.2.5](#).
- e Includes clinical chemistry (same as footnote d but excluding phosphate, cystatin, and uric acid); hematology (same as footnote d); and routine urinalysis (same as footnote d). It is strongly recommended that patients come to the study visit in a fasted state, and patients should remain fasted until their blood samples have been collected. If the patient has not been fasting, it should be documented accordingly in the eCRF.
- f Includes total cholesterol, LDL (direct), HDL (direct), and triglycerides (direct). Lipid analytes are shown in [Section 15.2.5](#)
- g Urine protein excretion and creatinine. Sample will be collected 24 hours immediately prior to the visit. Patients who forget to collect this sample 24 hours immediately prior to the visit may collect and return it within the visit window. Protein excretion and creatinine will be measured from this sample.
- h Patients will complete the KDQoL-36t. All patients will also complete the EQ-5D-5L. Patients participating in the OLE period who did not complete the questionnaires at Day 1 of the double-blind period should complete them at Week 114 (as baseline assessments for the OLE) and throughout the OLE.

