b Vital signs should be measured prior to having blood drawn for laboratory evaluations. Blood pressure will be measured after patients have been sitting comfortably in a chair for at least 5 minutes prior to obtaining 3 readings using the same arm for each reading; the mean of the last 2 readings will then be recorded. Measurements of blood pressure intended to detect possible orthostatic hypotension will also be performed at each visit (see [Section 9.6](#)). For these measurements, blood pressure will be measured

- 3 times: 1 time after the patient has been in a supine position for 5 minutes, 1 time after the patient has been standing for 1 minute, and 1 time after the patient has been standing for 3 minutes. Weight, heart rate, temperature, and respiration rate will also be recorded. Heart rates will be measured with each positional blood pressure reading for orthostatic hypotension detection.
- c Includes clinical chemistry (serum sodium, potassium, chloride, bicarbonate, total protein, albumin, calcium, phosphate, glucose, cystatin, uric acid, BUN, creatinine [including calculation of eGFR], bilirubin [total, direct, and indirect], ALT, AST, ALP, gamma glutamyltransferase, creatine kinase, and amylase); hematology (red blood cells, hemoglobin, hematocrit, MCV, MCH, MCHC, platelets, WBC, and WBC differential [percentage and absolute: neutrophils, eosinophils, basophils, lymphocytes, and monocytes]), and routine urinalysis (color, appearance, and dipstick [pH, specific gravity, protein, glucose, ketones, bilirubin, blood, urobilinogen, and leukocyte esterase]). All chemistry, hematology, and urinalysis analytes are shown in [Section 15.2.5](#).
  - d Includes total cholesterol, LDL (direct), HDL (direct), and triglycerides (direct). Lipid analytes are shown in [Section 15.2.5](#)
  - e Urine protein excretion and creatinine. Sample will be collected 24 hours immediately prior to the visit. Patients who forget to collect this sample 24 hours immediately prior to the visit may collect and return it within the visit window. Protein excretion and creatinine will be measured from this sample.
  - f Patients will complete the KDQoL-36. All patients will also complete the EQ-5D-5L.

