**Table 15.1-5. Sparsentan + SGLT2 Inhibitor Sub-study: Schedule of Study Events**

Please see information contained within the open-label extension Schedule of Study Events ([Table 15.1-3](#)).

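### UA/C is a named efficacy endpoint of the SGLT2 inhibitor Sub-study, but the open-label 24-hour urine panel contains no albumin, so UA/C cannot be calculated from the schedule as written

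*Protocol*

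**What the plan says.** Section 6.1.5.2 of the protocol lists, first among the Sub-study efficacy endpoints, "The mean percent change from Sub-study baseline in UP/C and UA/C based on a 24-hour urine sample at the next scheduled visit". The synopsis also names UA/C, with slightly different wording: "The mean change from Sub-study baseline in UP/C and UA/C based on a 24-hour urine sample at the next scheduled visit". The abbreviation list defines UA/C as "Urine albumin/creatinine ratio".

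Table 15.1-5, the Sub-study schedule, contains no assessments of its own. It reads "Please see information contained within the open-label extension Schedule of Study Events" and points to Table 15.1-3.

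For the 24-hour collection, footnote g of Table 15.1-3 and footnote e of Table 15.1-4 both state: "Urine protein excretion and creatinine. Sample will be collected 24 hours immediately prior to the visit". Both end with "Protein excretion and creatinine will be measured from this sample". Table 15.2-2, the open-label laboratory list, gives the same two analytes under 24-hour quantitative urinalysis.

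The double-blind schedule differs. Footnote f of Table 15.1-2 states "Protein and albumin excretion, creatinine, sodium, and urea will be measured from this sample". Footnote g of Table 15.1-1 and Table 15.2-1 also include urine albumin.

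**The concern.** A ratio endpoint needs both of its components measured. For UA/C the denominator (urine creatinine) is assayed in the open-label period, but the numerator (urine albumin) is not on any open-label list. If sites and the central laboratory follow the schedules, no Sub-study patient has a urine albumin value at baseline or at follow-up.

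The Sub-study is a randomized comparison whose efficacy question is the effect on proteinuria of adding an SGLT2 inhibitor to sparsentan, and UA/C is one of the two ratio measures named for it. An endpoint named in advance would have no data and would have to be explained as such in the study report. The protocol gives no assured way to recover the values afterwards.

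**Working it through.** No power or alpha figure is involved. The check is whether the scheduled assays supply what the endpoint needs.

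**Step 1: 24-hour urine analytes in each place that lists them.**

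| Protocol location | Period | Analytes | Urine albumin |
|---|---|---|---|
| Table 15.1-1, footnote g | Double-blind, screening to Week 36 | protein, albumin, creatinine, sodium, urea | yes |
| Table 15.1-2, footnote f | Double-blind, Weeks 48 to 114 | protein, albumin, creatinine, sodium, urea | yes |
| Table 15.2-1 | Double-blind laboratory list | protein, albumin, creatinine, sodium, urea | yes |
| Table 15.1-3, footnote g | Open-label, Weeks 110 to 186, and Sub-study | protein, creatinine | no |
| Table 15.1-4, footnote e | Open-label, Weeks 198 to 270 | protein, creatinine | no |
| Table 15.2-2 | Open-label laboratory list | protein, creatinine | no |

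The three open-label entries agree with one another, so this is not a single slip or a damaged table. The three double-blind entries show that the protocol names urine albumin where it wants it.

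**Step 2: which list governs the Sub-study samples.** Tables 15.1-3 and 15.1-4 place the Sub-study baseline between Week 126 and Week 258. The next scheduled visit is 12 weeks later, so follow-up falls between Week 138 and Week 270. Every Sub-study sample is therefore taken under the open-label lists.

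**Step 3: which endpoints can be derived.**
- UP/C = urine protein / urine creatinine: both measured, so it can be derived.
- Protein excretion <0.3 g/day: protein measured, so it can be derived.
- UA/C = urine albumin / urine creatinine: numerator not measured, so it cannot be derived.

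**Step 4: whether another source fills the gap.**
- The albumin in Panel A and Table 15.2-2 is under clinical chemistry, that is, serum albumin.
- The routine dipstick reports protein, not albumin.
- Biorepository urine (Section 9.12) depends on separate consent, and no UA/C assay is planned on it.
- Urine albumin measured at Weeks 110 and 114 under the double-blind schedule predates the earliest Sub-study baseline (Week 126).
- The SAP is written to Amendment 5 (SAP Section 5.4). The Sub-study came in with Amendment 6 (Protocol Appendix C), so the SAP does not cover it.

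**Step 5: extent.** About 60 patients × 2 time points (baseline and next scheduled visit) = about 120 samples, if every patient provides both collections.

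**The case against.** The strongest reply is that the protocol gives competing instructions, not a clear instruction to omit albumin. Section 9.8 covers laboratory work in general and includes albumin excretion among the analytes from the 24-hour samples, and its reference to the schedules could concern visits and not analytes. No open-label footnote uses the word only. Table 15.1-3 overlaps Table 15.1-2 at Weeks 110 and 114, where albumin is assayed from the 24-hour collection, so footnote g is not a complete list for those two visits. Section 9.8 also leaves sample details to central-laboratory instructions that are not in these documents, so what the laboratory actually runs is unknown.

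Part of this stands. The laboratory may in practice assay albumin, and the overlap shows that footnote g is not exhaustive at two visits. But neither point supplies the assay where it is needed. In Section 9.8 the words covering both study periods belong to the fasting sentence; the analyte sentence comes later and defers to the schedules, which specify no albumin in the open-label period. The overlap ends at Week 114, before any Sub-study baseline. An unseen laboratory instruction cannot cure a contradiction within the protocol.

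The objection on importance also stands in part. Section 12.2 gives the Sub-study sample size no formal statistical basis, Section 12.12 plans descriptive summaries, and UP/C addresses the proteinuria question without UA/C.

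**Conclusion.** The concern holds. Followed as written, the open-label schedules leave UA/C without data for all of the roughly 60 Sub-study patients at both time points. This assumes that the laboratory assays what the schedules and Table 15.2-2 list and nothing more from Week 126 onward.

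The point is best read as an internal inconsistency. A plausible origin, though an inference, is that the open-label panel was built for endpoints using UP/C only (Section 6.1.4) and was not extended when Amendment 6 added the Sub-study. It should be corrected, but it threatens no conclusion of the main trial, no hypothesis test depends on UA/C, and the other Sub-study proteinuria endpoints are unaffected.

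**What to change.** Choose one of two changes:

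1. **Keep UA/C.** Add urine albumin to the 24-hour urine analytes for the Sub-study baseline and next scheduled visit, in Table 15.1-3 footnote g, Table 15.1-4 footnote e and Table 15.2-2. Section 9.8 then agrees with the schedules for these samples.
2. **Drop UA/C.** Delete it from Section 6.1.5.2 and from the Sub-study endpoints in the synopsis.

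The first option costs one extra central-laboratory assay on about 120 samples that are already collected, plus footnote and table wording. It needs no new visit or procedure. The baseline sample is taken at the eligibility visit, before randomization, so the number of assays would be somewhat higher if albumin is run on everyone screened for the Sub-study. The second option costs wording only. If the laboratory already runs albumin under its own instructions, the protocol lists still need to say so.

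The same edit should settle whether the endpoint is a mean change (synopsis) or a mean percent change (Section 6.1.5.2).

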## **6.2. Study Design**

This is a 114-week, randomized, multicenter, double-blind, parallel-group, active control study, with an open-label extension period of up to 156 weeks for a total study duration of up to 270 weeks in patients with IgAN who have persistent overt proteinuria and remain at high risk of disease progression despite being on a stable dose (or doses) of an ACEI and/or ARB that is (are) a maximum tolerated dose that is at least one-half of the maximum labeled dose (MLD) (see Appendix B, [Section 15.2.3](#)). The dose must have been stable for at least 12 weeks prior to study entry. Approximately 380 patients will be enrolled into the study. Additionally, there is an optional Sub-study during the open-label extension period that is 12 weeks in duration and is anticipated to enroll approximately 60 patients (see [Section 6.2.3](#) for additional details).

### **6.2.1. Double-blind Period Design**

Patients who meet eligibility criteria and provide written informed consent will undergo comprehensive baseline evaluations and clinical laboratory tests and will be randomly assigned in a 1:1 ratio to receive either sparsentan or active control (irbesartan). Randomization will include stratification by eGFR value ( $30$  mL/min/ $1.73$  m^2 to  $<60$  mL/min/ $1.73$  m^2 and  $\geq 60$  mL/min/ $1.73$  m^2) and urine protein excretion ( $\leq 1.75$  g/day and  $>1.75$  g/day).

Standard-of-care treatment (ACEI and/or ARB therapy) and any other prohibited concomitant medications will be discontinued before the randomization (Day 1) visit. The final dose of an ACEI and/or ARB should be taken on the day before the randomization (Day 1) visit (see [Section 15.2.1](#)). The study medication (sparsentan or irbesartan) will be initiated on Day 1 according to [Section 8.1](#). Throughout the study (including the open-label extension period), patients will be maintained on the maximum allowed dose of study medication they can

tolerate while secondarily maintaining blood pressure as close as possible to the target level of 125/75 mmHg. This blood pressure target is in line with the KDIGO Clinical Practice Guideline (KDIGO 2012). Treatment with additional anti-hypertensive agents is encouraged during the study, with the exception of those that inhibit the RAAS (ACEIs, aldosterone blockers, aliskiren, or ARBs) and endothelin systems (ERAs; eg, ambrisentan, bosentan).

It is recommended that systemic corticosteroid and/or immunosuppressive therapy for the treatment of IgAN be avoided for the duration of participation in the study. If, in the Investigator's opinion, systemic corticosteroid and/or immunosuppressive therapy is warranted, such intervention may be provided in addition to study medication at the discretion of the Investigator. Consultation with the Medical Monitor is recommended before starting interventional therapy, when possible. Such interventions (including the duration and outcome of treatment) should be documented on the electronic case report form (eCRF).

Study visits will be conducted at 2, 4, 6, and 12 weeks after randomization and at approximately 12-week intervals thereafter. Following the 110-week blinded treatment period, treatment with study medication will be discontinued for 4 weeks. At this time, the Investigator should resume standard-of-care treatment, including RAAS inhibitor treatment. Where possible, the same treatment regimen the patient was on at study entry (ie, the same ACEI and/or ARB at the same dose[s]) should be used unless, in the Investigator's opinion, an alternative treatment approach is warranted. The Investigator may make additional adjustments in anti-hypertensive medications if considered necessary to adequately control blood pressure. Patients will return to the site for the Week 114 visit after study medication has been discontinued (see [Table 1](#) and [Section 15.1](#)).

[figure not shown]
Patients who complete the double-blind period may be eligible to enroll in the open-label extension period.

Sparsentan or irbesartan concentrations (and possibly metabolites) in plasma will be evaluated. At specified visits, 1 trough sample will be obtained pre-dose in the clinic.

The primary analysis of proteinuria will be performed after the last patient randomized has undergone the Week 36 visit. Subsequently, all patients will continue to be followed on an intent-to-treat basis to Week 114 for the longer-term assessment of eGFR rate of change. Unless otherwise specified, endpoints will use the last pre-treatment value available prior to the first dose of study medication as baseline.

Flow chart and table depicting the double-blind period are provided in [Figure 1](#) and [Table 1](#).

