#### **8.5. Method of Assigning Patients to Treatment (Randomization)**

This study will be conducted in a double-blind, active-controlled manner. Enrolled patients will be randomly assigned in a 1:1 ratio to sparsentan or the active control (irbesartan) in the double-blind period, based on a predefined randomization code (generated by the Sponsor or designee) via the interactive randomization technology (IRT) at the Day 1/Randomization visit. Randomized patients will be stratified by their screening eGFR value (30 to <60 mL/min/1.73 m^2 and ≥60 mL/min/1.73 m^2) and screening urine protein excretion (≤1.75 g/day and >1.75 g/day).

The Sub-study will be conducted in an open-label, randomized manner. Enrolled patients will be randomly assigned in a 1:1 ratio to receive either SGLT2 inhibitor treatment or no SGLT2 inhibitor treatment, based on a predefined randomization code (generated by the Sponsor or designee) via IRT at the Sub-study Screening/Randomization/Day 1 visit.

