## **12.7. Efficacy Analyses**

Efficacy analyses during the double-blind period will be based on the FAS. The primary and key secondary endpoint analyses only will be repeated in the PP Analysis Set as supportive analyses.

As UP/C is a highly right-skewed variable, analyses will be performed on log-transformed data.

The eGFR for each time point (visit) will be determined using the CKD-EPI (Levey 2009) formula for adults based on age, sex, race, and serum creatinine values from the visit. The eGFR will be determined at screening and at assessment time points detailed in the Schedules of Study Events (Section 15.1).

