### **6.4. Baseline Definition**

#### **6.4.1. Double-Blind Baseline**

Double-blind baseline is defined as the last nonmissing assessment prior to and including the first administration of study medication (including unscheduled assessments) in the study. In the case where the last nonmissing assessment and the study medication start date (and time if available) coincide, that assessment will be considered baseline. Unless explicitly stated, all baseline used in this SAP will refer to the double-blind baseline.

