#### **8.4.3. Procedure for Testing Other Secondary Endpoints Within the US and Non-US Countries**

At the time of the final (confirmatory) analysis, if all the key secondary endpoints achieve statistical significance within the US or non-US countries, the other secondary endpoints will be statistically tested at the available alpha in the order specified below:

1. The mean change from baseline in UP/C at Week 110
2. The mean change from baseline in urine protein excretion at Week 110
3. The mean change from baseline in UA/C at Week 110
4. The mean change from baseline in urine albumin excretion at Week 110
5. The proportion of patients reaching a confirmed 40% reduction in eGFR, ESRD, or death
6. The mean change from baseline in eGFR at Week 110

The multiple testing strategies for the US and for non-US countries are shown in [Figure 1](#).

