### **8.7.2. Change in eGFR from Baseline to 4 Weeks Post-cessation of Randomized Treatment (Week 114)**

The change from baseline to 4 weeks post-cessation of randomized treatment (114 weeks) will be analyzed via analysis of covariance (ANCOVA). The dependent variable will be the change from baseline eGFR at the analysis visit at Week 114. The model will include the following fixed effects:

- Treatment group (2 levels: sparsentan, irbesartan)
- Baseline eGFR
- Randomization stratification variable (4 levels based on Screening eGFR and urine protein excretion)

The treatment effect will be the contrast between sparsentan and irbesartan LS means. The LS means, treatment effect estimate (difference in LS means), 95% CI, and p-value will be presented.

Robustness of the analysis due to missing data and premature treatment discontinuations will be explored by assessing the change from baseline to 4-weeks post EOT analysis visit.

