### **8.7.3. Other Continuous Endpoints**

The following exploratory endpoints will be analyzed using an MMRM as described for the primary efficacy endpoint ([Section 8.5.1](#)). Missing data will not be imputed using the MI procedure:

- The mean change from baseline in eGFR and selected proteinuria variables, based on a 24-hour urine sample (eg, urine protein excretion, urine albumin excretion, UA/C, and UP/C), up to Week 110
- Mean changes from baseline in QoL, measured via PRO at each visit
- Change from baseline for blood pressure will also be analyzed at both primary analysis and at final analysis.

The following exploratory endpoints will be analyzed using an ANCOVA analysis:

- The change from baseline in eGFR at 6 weeks post randomization (ie, the acute effect of randomized therapy)
- The change from EOT (ie, Week 110) in eGFR 4 weeks following cessation of treatment (ie, at Week 114)
- Duration of hospitalizations (for any reason and for reasons related to the kidney)

Specifically, the change from baseline or EOT or duration (as applicable) will be the dependent variable, treatment group, and randomization stratification strata as fixed effects and baseline value as covariate. The treatment effect will be the contrast between sparsentan and irbesartan LS means. The LS means, treatment effect estimate, 95% CI, and p-value will be presented.

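### The eGFR change analyses adjust for one continuous pre-dose eGFR; where a separate Screening value exists, adding it would modestly sharpen three other secondary or exploratory contrasts

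*Protocol*

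**What the plan says.** Baseline is one value in both documents. Protocol 6.2.1 states: "Unless otherwise specified, endpoints will use the last pre-treatment value available prior to the first dose of study medication as baseline". SAP 6.4.1 agrees: "Double-blind baseline is defined as the last nonmissing assessment prior to and including the first administration of study medication".

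The eGFR change models are as follows:

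- **Baseline to Week 114 (SAP 8.7.2, Protocol 12.7.4).** ANCOVA with treatment, baseline eGFR and "Randomization stratification variable (4 levels based on Screening eGFR and urine protein excretion" as a four-level factor.
- **Week 6 (SAP 8.7.3, Protocol 12.7.4).** ANCOVA with "treatment group, and randomization stratification strata as fixed effects and baseline value as covariate".
- **Change over time to Week 110 (SAP 8.7.3).** MMRM built like the primary analysis: one continuous baseline plus the strata. Its Week 110 contrast, "The mean change from baseline in eGFR at Week 110", is sixth and last in the ordered list of other secondary tests in SAP 8.4.3.

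Screening eGFR reaches these models only in coarse form. Protocol 8.5 says "Randomized patients will be stratified by their screening eGFR value", with one cut at 60 mL/min/1.73 m².

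On availability, Protocol 12.7 says "The eGFR will be determined at screening and at assessment time points detailed in the Schedules of Study Events". Table 15.1-1 marks Panel A (which includes creatinine) and the eGFR calculation at both Screening and Day 1, with Screening up to 28 days earlier. Footnote g to that table waives the Visit 2 sample, and with it the eGFR calculation, when the screening sample was collected in the 14 days before Visit 2.

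**The concern.** A single eGFR is a noisy measure of a patient's level. The documents' own residual error is 5.8 mL/min/1.73 m². Noise in the one baseline covariate passes into the residual of each change analysis and widens the treatment contrast. A second reading taken before randomized drug would remove part of that noise. Because it precedes randomization, it cannot systematically favour either arm. Cutting it at 60 discards most of its information.

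What is at stake is precision in three analyses: the Week 110 eGFR change, the acute effect at Week 6, and the off-treatment change at Week 114. The last two bear on whether an eGFR difference reflects a reversible haemodynamic effect or preserved function.

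**Working it through.** **Inputs from the documents.** N = 380, 1:1 allocation, residual SD σ = 5.8, strata cut at 60, Screening eGFR at least 30.

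**Inputs assumed.** Between-patient SD τ = 15 to 22, slope SD 3 to 5 mL/min/1.73 m² per year, the share of patients with no separate Day 1 eGFR, the residual correlation, and no dropout.

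**1. The plan's own figure.** The documents give no power or variance for the change analyses. Their eGFR figure is for total slope: 380 patients, 2.9 per year, 90% power, one-sided α = 0.02. The implied SE is 2.9 / (2.054 + 1.282) = 0.869. From that SE:

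- power at 2.55 is Φ(2.55/0.869 − 2.054) = 81.0% (stated 80%);
- power at 3.15 is 94.2% (stated above 90%);
- the smallest significant difference is 2.054 × 0.869 = 1.79 (stated 1.8).

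With SE = 5.8 × √(2/190) / SD(time), a Day 1 plus roughly 12-weekly schedule has SD(time) = 0.690 years and gives 90.4% power with N = 376. The 5.8 is therefore used as a within-patient residual SD, and it is used the same way below.

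**2. Closed form without strata.** Take independent residuals and τ = 20, so τ² = 400 and σ² = 33.64. The residual variance of the follow-up value is:

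- one baseline: τ² + σ² − τ⁴/(τ² + σ²) = 433.64 − 160000/433.64 = 64.7;
- two baselines: τ² + σ² − 2τ⁴/(2τ² + σ²) = 433.64 − 320000/833.64 = 49.8.

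At Week 6 that is a 23% drop. At Week 110, slope variation adds about 40 to both figures for slope SD 3 (104.7 to 89.8, or 14.2%) and about 111 for slope SD 5 (175.8 to 160.9, or 8.5%). Week 114 is slightly lower than Week 110, at 13.8% and 8.1%.

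**3. With the strata already in the model.** The cut at 60 has captured part of this gain. Simulation of the planned ANCOVA with and without continuous Screening eGFR gave, at τ = 20 and Week 6, an SE of 0.797 falling to 0.728. The variance ratio is (0.728/0.797)² = 0.83, so the drop is about 17% and not 23%. Across scenarios:

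| Patients without a separate Day 1 eGFR | 4-week residual correlation | Week 6 variance drop | Week 110 variance drop |
|---|---|---|---|
| None | 0 | about 14–17% | about 5–10% |
| Half | 0 | about 8–10% | about 3–6% |
| Half | 0.5 | about 1–2% | about 1–3% |
| All | any | 0% | 0% |

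The second row uses a slightly wider range for τ, 15 to 25. In the third row the Week 6 figure depends on how the correlation is carried past Day 1; one variant gave about 2.5%. As an equivalent number of patients, a 17% drop is 1/0.83 = 1.20, or 20% more, and a 2% drop is 1/0.98 = 1.02, or 2% more.

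**4. Slope endpoints.** In those models baseline eGFR is a main effect only. With balanced visits, a further main-effect covariate leaves the treatment-by-time contrast untouched. The slope SE was 0.407 (slope SD 3) and 0.578 (slope SD 5) both with and without it.

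**The case against.** The strongest objection is availability. Screening runs up to 28 days, so the 14-day waiver in footnote g could cover a large share of patients. For them the baseline is the Screening value and a second covariate adds nothing. This stands: a reader might infer from the visit schedule that every patient has two values, and the documents do not support that. They do not settle the opposite either. Footnote g hangs on the 24-hour urine row, while the Panel A and eGFR rows on Day 1 carry no waiver of their own.

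Second, between-patient SD, slope SD and residual correlation are not in the documents. The 5.8 is scatter around a fitted registry line, not shown to be independent noise between two samples weeks apart. The Week 110 figure comes from a single-visit ANCOVA, whereas the plan uses an MMRM on on-treatment data. This also stands, and it is why the gain is given as a range that reaches zero.

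Third, nothing decisive is touched. Week 6 and Week 114 are exploratory. Week 110 eGFR change is tested only after all key secondary endpoints and five other tests succeed. That is correct and fixes the weight of the point.

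Fourth, adjusting for one baseline plus strata is valid. That is also correct: the issue is unused precision, not bias.

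**Conclusion.** The point holds as a small, optional improvement. The three eGFR change analyses use one continuous pre-dose eGFR and leave a second one unused wherever it exists. The variance reduction is about 14–17% at Week 6 and 5–10% at Week 110 in the favourable case, about 1–2% and 1–3% with half the Day 1 values skipped and a correlation of 0.5, and nil if all are skipped. It was never negative in the scenarios run. These figures rest on the assumed SDs and correlations listed above and on no dropout.

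Three stronger readings should be resisted. The gain does not reach the key secondary slope endpoints, because a main-effect covariate leaves those contrasts unchanged. The primary UP/C analysis is not part of the point. And the change is not wholly free: it takes a degree of freedom, a rule for patients with one value, a definition of which Screening value counts, and specification before unblinding.

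**What to change.** In SAP 8.7.2 and 8.7.3 and Protocol 12.7.4:

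1. State that Day 1 eGFR is derived from Panel A creatinine whenever that sample is drawn, which also settles how footnote g is to be read.
2. In the eGFR MMRM and in the Week 6 and baseline-to-Week-114 ANCOVAs, add continuous Screening eGFR beside baseline eGFR. Define it as the last central value before Day 1 from the screening that led to randomization, since repeat measurements and re-screening are allowed. Alternatively, use the mean of all central pre-dose eGFR values as the covariate.
3. State that a patient with one pre-dose value uses it for both.
4. Specify this before the relevant unblinding. SAP 5.1 has select efficacy endpoints analysed unblinded at the primary analysis, so that is the first deadline.

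Endpoint definitions, strata and slope models stay as they are. The cost is one degree of freedom out of about 374 and SAP wording, with no new data.
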